### 3.3. Specific Aim #3: To determine the effects of the LoBAG30 diet compared to the control diet on the composition of the gut microbiome.

Stool samples collected before and after diet intervention will be used for species analysis of the gut microbiome. We hypothesize that there will be a change in the gut microbiome following the LoBAG30 diet when compared to the control diet, and that this change will be associated with characteristics expected to provide metabolic benefit to subjects with DM2. These changes might include increased species diversity and increased relative abundance of species associated with a healthy microbiome profile. If funding can be secured, we will also analyze bacterial metabolites to determine if there are potentially beneficial increases in short chain fatty acids and secondary bile acids with the LoBAG30 diet.

## 4. Research Plan

An overview of the proposed study design is shown in **Figure 1**. A detailed study timeline is included as an appendix to this document.

**Figure 1.** Overview of proposed study design.

### 4.1. Study cohort

Up to 70 men and women with DM2 will be recruited and enrolled (dependent on funding), for a goal of 44 participants completing the trial.

To be eligible, subjects must be  $\geq 18$  years of age, have a previous diagnosis of DM2 by ADA criteria (20) and have a HgbA1c of 7.0-9.5% while either taking no medications for diabetes or using metformin alone.

Exclusion criteria will be:

- 1) type 1 diabetes mellitus,
- 2) treatment with insulin,
- 3) BMI <25 kg/m^2,
- 4) lack of weight stability defined as a change in weight of more than 5 pounds in the prior 3 months,
- 5) estimated glomerular filtration rate < 60 ml/minute/1.73 m^2,
- 6) urine albumin >300 mg/g creatinine,
- 7) pregnancy or immediate plans to become pregnant,
- 8) breast feeding,
- 9) dietary restriction(s) that would preclude consumption of study diets,
- 10) inability or unwillingness to prepare meals,
- 11) anemia, which would affect interpretation of HgbA1c,
- 12) presence of any disease which would make adherence to the study protocol difficult, and
- 13) use of antibiotics in the 3-month period prior to enrollment.

Subjects will be recruited from the University of Minnesota and surrounding communities. In addition, potential subjects will be identified from the Fairview patient population using Informatics Consulting Services (ICS) through the CTSI, and mailed letters informing them of possible study eligibility by the Fairview Research Administration.

#### **4.2. Outcome Measures**

The primary endpoint will be HgbA1c at the end of the 12 week diet intervention period. Secondary endpoints will be:

- 1) Weight
- 2) Fasting plasma glucose
- 3) Fasting serum insulin
- 4) Postprandial glucose response at +30, +60, +90, +120, +180 and +240 minutes following the start of a meal consistent with the assigned diet
- 5) Postprandial insulin response at +30, +60, +90, +120, +180 and +240 minutes following the start of a meal consistent with the assigned diet
- 6) Fructosamine
- 7) Fasting serum lipids
- 8) Stool samples for microbiome species analysis. Samples will also be saved for possible bacterial metabolite analysis.
- 9) Glucose variability as measured by continuous glucose monitoring (CGM).

#### **4.3. Intervention**

A randomized, controlled, parallel group design will be used to compare the effects of the LoBAG30 diet or a balanced diet consistent with current ADA guidelines on our outcomes. Dietary intervention periods will be 12 weeks long. Both the LoBAG and control diets will consist of common foods.

Subjects will be asked to keep their physical activity level constant during the study. Medications for diabetes will be continued without change during the study. Medications will be monitored, and if a participant's medications are altered this will be noted. If antibiotics are used during the study this will be recorded. Subjects will be instructed that they do not need to monitor blood sugars regularly at home.

After enrollment and consent subjects will be randomized in a 1:1 allocation ratio to the LoBAG30 diet or a balanced diet consistent with ADA guidelines. Randomization will be stratified by diabetes treatment at enrollment (no glycemic medications or metformin) and by HgbA1c (7.0-8.5% or 8.5-9.5%), and implemented within stratum using randomly permuted block sizes of 2 and 4. If closely related subjects choose to enroll together (for example spouses or subjects that live together, and would typically share meals) they will be randomized to the same study arm. Baseline measures will be collected. Subjects will meet individually with the study dietitian, who will provide diet instruction, sample menus, and recipes consistent with the assigned diet. Dietitian consultation may be conducted

in person or by phone. During week 2 subjects will have a repeat consult with the dietitian to reinforce diet instruction. If weight has changed caloric intake will be adjusted as necessary for a goal of weight stability. A midpoint visit will be conducted at week 6, during which subjects will provide a blood sample, urine sample, and a stool sample, and will consult with the dietitian for reinforcement of diet advice. If weight has changed caloric intake will be adjusted to prevent further change. Midpoint blood and stool samples will be stored and analyzed in the future based on available funding. At week 9 subjects will consult with the study dietitian for reinforcement of diet advice and collection of a urine sample to assess compliance. The final study visit will be at the end of week 12. All outcome measures will be assessed at the final visit.

If funding is available continuous glucose monitoring (CGM) will be added at the beginning and end of the study intervention. Subjects will be asked to wear the Freestyle Libre Pro CGM system for 2 weeks following the screening visit (visit 1) and for 2 weeks between visit 5 and visit 6. The CGM sensor will be worn on the back of the arm and will monitor and record interstitial glucose continuously throughout periods of CGM use. Subjects will be blinded to CGM glucose data. Sensors will be returned to study staff by mail or in person at study visits. Subjects will be given the option to receive a copy of CGM data, and to review this data with study staff, at the final study visit.

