## Appendix 1: Timeline and Details of Study Visits

**Screen.** No visit needed. Will usually be done by telephone; may also be done by email or in person. (20 minutes)

**Visit 1.** Consent and Screening Visit. (1 hour)

- Review consent document and obtain informed consent.
- Collect baseline compliance survey, Diet Satisfaction Questionnaire, and Diabetes Treatment Satisfaction Questionnaire. Can alternatively be collected at visit 2.
- Measure weight and height.
- Non-fasting blood draw (for HgbA1c, basic metabolic panel, and complete blood count)
- Collect urine sample (for baseline urine nitrogen and urine creatinine, urine microalbumin, and pregnancy test if female and premenopausal).
- Send home with 3-day food intake diary (to be used by the study dietitian for caloric planning; the same food diary will also be collected at visit 4 and visit 6).
- If funding allows, place Abbott Freestyle Libre CGM. Provide supplies to return the CGM sensor (by mail or in person).
- Provide stool collection kit. Give instruction in stool sample collection.

Details for stool sample collection:

- Subject self-collects at home by sampling a stool with a sterile swab and putting the sample in a collection tube containing a preservative.
- This room-temperature-stable sample can be delivered to study investigators by the subject at study visits, or can be returned through the mail.
- Study staff will put the de-identified sample into the CTSI storage freezer.

**Randomization.** No visit needed.

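### The two HgbA1c randomisation strata both include 8.5%, so the written rule does not say which list a participant at that value belongs to

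*Combined protocol and SAP*

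**What the plan says.** All references are to the combined protocol and SAP.

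- **Eligibility (section 4.1).** Participants must "have a HgbA1c of 7.0-9.5% while either taking no medications for diabetes or using metformin alone". A value of 8.5% is therefore eligible.
- **Stratification (section 4.3).** The HgbA1c factor is written as "by HgbA1c (7.0-8.5% or 8.5-9.5%), and implemented within stratum using randomly permuted block sizes of 2 and 4". The other factor is whether the participant is untreated or on metformin. Two factors with two levels each give four lists.
- **Allocation (section 4.3).** After consent, "subjects will be randomized in a 1:1 allocation ratio".
- **Timing (Appendix 1).** The Visit 1 procedures include "Non-fasting blood draw (for HgbA1c, basic metabolic panel, and complete blood count"). Randomisation is listed after Visit 1 as a step that needs no visit, so the HgbA1c result can be known when the stratum is assigned.
- **Visibility of the arm (section 4.3).** "Subjects will meet individually with the study dietitian, who will provide diet instruction, sample menus, and recipes consistent with the assigned diet". The only blinding described is "Subjects will be blinded to CGM glucose data", which concerns sensor readings and not the diet.
- **Analysis (section 4.7).** Paired t-tests are planned within participants and unpaired t-tests between diets. No planned analysis uses the strata.

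Section 4.9 mentions stratified randomisation only for medication use and does not settle the boundary. Appendix 2 (the COVID-19 procedures) does not settle it either.

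**The concern.** A stratification rule should place every eligible participant in exactly one list, and this one fails at a single value. That value is a result for the baseline of the primary endpoint, and it is available before allocation.

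What is at stake is allocation discretion. If a person decides which list a participant at 8.5% enters, and that person knows the allocations already made in both lists, small blocks make the next assignment partly predictable. Choosing the list then shifts the odds of a particular arm. Even without any such intent, two staff members could place the same value differently, and the stratum used would not be recoverable from the protocol.

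A related gap is that the strata built into the randomisation are not used in the between-group comparison.

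**Working it through.** The plan states no figure on this point, so there is none to reproduce. The check has three parts.

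**1. Is there an overlap?** The ranges are [7.0, 8.5] and [8.5, 9.5]. Their intersection is the single value 8.5. It lies inside the eligible range 7.0-9.5, and no section assigns it to one side.

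**2. How many participants could be affected?**

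Inputs:
- Number randomised, lower figure: 44, the goal for completers (section 4.1).
- Number randomised, upper figure: section 4.7 expects up to 70 recruited and reports that 8 of 12 pilot enrolees were eligible. 70 x 8/12 = 46.7, or about 47.
- Share at exactly 8.5%: not in the documents, so assumed. If results are reported to 0.1%, there are 26 values from 7.0 to 9.5, and an even spread gives 1/26 = 3.8%. A share of 1% is taken as a low alternative.

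Expected number = N x share. Chance of at least one = 1 - (1 - share)^N.

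| N | Share | Expected at 8.5% | Chance of at least one |
|---|---|---|---|
| 44 | 1% | 0.44 | 1 - 0.99^44 = 36% |
| 47 | 1% | 0.47 | 1 - 0.99^47 = 38% |
| 44 | 1/26 | 1.7 | 1 - (25/26)^44 = 82% |
| 47 | 1/26 | 1.8 | 1 - (25/26)^47 = 84% |

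With N = 47 and a share of 1/26, the binomial probability of 4 or fewer such participants is 97%. This supports 0 to 4 as the likely count. At a 6% share, the expected number among 47 is 2.8.

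**3. What is the most that choosing the list could achieve?** This was simulated (20,000 runs) under worst-case assumptions: block sizes 2 and 4 equally likely, 0 to 17 prior allocations in each list, all of them known, and exact Bayesian prediction of the next one.

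- Correct guess of the next allocation in one list: about 72%.
- The two candidate lists differ in predicted probability: about 78% of the time.
- Chance of a preferred arm: 50% with no choice of list, about 67% when the more favourable list is chosen.

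The gain is 67 - 50 = 17 percentage points for each affected participant. Over 1.7 to 1.8 participants this is 0.17 x 1.7 to 0.17 x 1.8, or about 0.3 participants redirected in the whole trial. With 8.5% in one stratum only, the figure returns to 50%.

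**The case against.** The strongest reply is that this is a slip of boundary notation and that the documents do not show the harm.

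- **Nothing says that staff choose the list.** The documents do not state who assigns the stratum, whether a system applies a coded cut-off, or who can see prior allocations. This stands, so the allocation risk is conditional. It does not remove the gap in the text: if a cut-off is coded, the protocol should state it.
- **A reader might infer that choosing the stratum amounts to choosing the arm.** The documents do not support that. It would need a value of exactly 8.5%, discretion over the list, knowledge of both lists, and intent. Only the first is shown to be possible. Even with all four, the odds move from 50% to about 67%.
- **A reader might infer that the problem is almost certain to arise.** An even spread with 70 randomised gives 1 - (25/26)^70 = 94%. However, the even spread is assumed, and 70 counts people recruited, including those lost at screening.
- **A reader might infer that a planned stratified analysis cannot be reproduced.** No such analysis is planned. Section 4.7 has only t-tests.
- **The term open-label is never used.** That is correct, but participants prepare the diet, the dietitian teaches it, and no blinding to diet is described. It is a fair inference that staff can see the arm.

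**Conclusion.** The point holds as a gap in the written rule. Both strata include 8.5%, that value is eligible, and no section resolves it. This part rests on the text alone and needs no assumption.

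The consequence is minor and conditional. The count of 0 to 4 participants and the 36% to 84% chance of at least one rest on an assumed share of 1% to 1/26 and on 44 to 47 randomised. Even in the worst case simulated, well under one participant would be redirected on average, so any effect on the treatment estimate is small. Nothing suggests that the overlap has been exploited.

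The missing stratum adjustment is a separate, inexpensive improvement and not a consequence of the overlap. The reason for it is that randomisation is balanced on factors that the comparison then ignores, one of which is the baseline level of the primary endpoint.

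**What to change.** 1. In section 4.3, define the HgbA1c strata as <8.5% and >=8.5%, based on the Visit 1 laboratory value. This form is safer than 7.0-8.4% and 8.5-9.5%, which would leave a gap for a result such as 8.45%; the documents do not state the reporting precision.
2. State who or what assigns the stratum and how the next allocation is concealed. If the randomisation system already codes a cut-off, make the text match it.
3. Record the stratum used for each participant, and document how any 8.5% value already randomised was placed. Do not reassign anyone.
4. In section 4.7, compare the diets on week-12 HgbA1c with a linear model that includes terms for the recorded randomisation strata, in place of the unadjusted unpaired t-test.

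The cost is a one-line amendment to section 4.3, a check of the randomisation form, one added data field, and a sentence in section 4.7 that should be settled before the outcome data are analysed. Sample size, power and alpha do not change.

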#### **4.7. Methods of Data Analysis**

The primary outcome will be HgbA1c at the end of the 12-week study period. Results will be compared pre and post diet intervention (within an individual subject) using paired t-tests and between dietary interventions (LoBAG30 versus control) using unpaired t-tests. Data will be analyzed at study completion.

Sample size was estimated a priori based on a two-tailed type I error of 0.05. For a difference of 1.5 points in HgbA1c and a power of 80%, 12 participants are required per intervention group. This number was increased by 30% to account for participant loss during screening, and an additional 30% to account for participant attrition, yielding 19 participants per intervention group (total 38 participants). An additional 12 participants have been enrolled using pilot funding from the University of Minnesota (of which 8 were eligible and 6 completed the entire study intervention).

This estimate uses preliminary data from existing LoBAG30 studies which were collected in a carefully controlled research setting. This differs from the conditions planned for this study. There are no data on the performance of the LoBAG30 diet in a free-living population of subjects with DM2. Thus, we will generate data that can be used to estimate effect size and variability for a power calculation for a future larger clinical trial.

With a goal of 38 plus 6 subjects completing the entire 12-week intervention, we anticipate recruiting up to 70 subjects in total.

If a subject withdraws from the study prior to study completion they will be invited to complete the final study visit prior to withdrawal, if possible. Any data collected from the subject prior to study withdrawal will be included in the final analysis. In the case of subject withdrawal an additional subject will be recruited to replace accordingly, dependent on funding.

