#### **4.9. Anticipated Problems and Proposed Solutions**

Although a free-living study cohort was purposefully chosen to answer the central question of this study, it is anticipated that compliance with study diets in this cohort will be lower than that in previous LoBAG diet studies. To address this, measures of compliance have been included, and frequent phone calls added to the protocol to encourage diet compliance. Although the dietary interventions in this study are meant to be weight stable, we acknowledge that weight change during the study may influence our results. For this reason, we have included three predetermined points in the protocol when caloric advice can be adjusted if indicated. Finally, use of medications for diabetes could impact the size of the effect of the LoBAG30 diet on HgbA1c, and so we have limited inclusion criteria to no glycemic medication or metformin only. We will also use stratified randomization to ensure equal distribution of medication use across study groups.

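### The between-arm unpaired t-test in 4.7 uses neither the stratified allocation nor the same-arm household rule in 4.3; a baseline-adjusted model would be a cheap, modest improvement

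*Combined protocol and SAP*

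**What the plan says.** Section 4.3 (Intervention) sets out 1:1 allocation, "stratified by diabetes treatment at enrollment (no glycemic medications or metformin) and by HgbA1c", with permuted blocks of 2 and 4 within stratum. It adds an exception: "If closely related subjects choose to enroll together", as spouses might, those who "would typically share meals) they will be randomized to the same study arm". For such subjects the household is the unit of allocation.

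Section 4.9 says that diabetes medication could affect the size of the diet's effect, and answers this by design: "We will also use stratified randomization to ensure equal distribution of medication use across study groups".

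Section 4.7 (Methods of Data Analysis) compares LoBAG30 "versus control) using unpaired t-tests". Neither that section nor any other names a stratum, a baseline covariate, a household term or a household identifier. Sections 4.2 and 4.7 define the primary outcome as HgbA1c at week 12, whereas section 2 and Specific Aim 1 (3.1) speak of a reduction. The quantity entering the unpaired test is therefore not fixed.

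**The concern.** A standard error should reflect how subjects were allocated. Two features here act in opposite directions.

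- Stratifying on a prognostic factor balances it between arms, so the true variance of the difference falls. A t-test that ignores the strata still counts that variance, and its standard error is too large. The HgbA1c stratifier is the baseline value of the primary endpoint, so it is plausibly prognostic.
- Placing two positively correlated household members in one arm raises the true variance. A t-test that treats them as independent has too small a standard error.

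At stake are the precision of the primary comparison and the nominal level of its p-value. The standard error also has a later use, because section 4.7 says "we will generate data that can be used to estimate effect size and variability for a power calculation" of a future larger trial.

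**Working it through.** **Inputs from the documents.** 44 completers (4.1), so 22 per arm; four strata, blocks of 2 and 4, and the household rule (4.3); two-sided alpha of 0.05 (4.7).

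**Inputs assumed, because the documents give none.** Correlation of baseline with week-12 HgbA1c (rho) 0 to 0.5; number of pairs 0 to 4, with 10 as an extreme; within-pair residual correlation (ICC) 0.1 to 0.5; baseline uniform on 7.0-9.5%, so its SD is 2.5/√12 = 0.72; 60% on metformin with no effect of its own; a pair takes one draw from its first member's stratum.

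**The plan's own figure.** Section 4.7 states that "12 participants are required per intervention group" for 1.5 points at 80% power, but gives no SD. Solving the two-sample t-test power formula backwards gives an SD of about 1.25. This is used below as one possible week-12 SD.

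**1. Strata ignored, no pairs, week-12 values.** Splitting a uniform baseline at 8.5 (40% above) keeps 3 × 0.6 × 0.4 = 0.72 of its variance, so the strata explain R² = 0.72 × rho². The t-test standard error is then 1/√(1 − R²) times the true one.

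| rho | R² | SE ratio | type I error, formula | type I error, simulated |
|---|---|---|---|---|
| 0.3 | 0.065 | 1.034 | 4.3% | about 4.5% |
| 0.5 | 0.180 | 1.104 | 3.1% | 3.1-3.3% |

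Mean 95% interval widths (SD units), t-test against the adjusted model:
- rho 0: 1.212 v 1.233, adjusted 2% wider
- rho 0.3: 1.211 v 1.174, adjusted 3% narrower
- rho 0.5: 1.215 v 1.066, adjusted 12% narrower

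**2. The same comparison against a change-score t-test.** Change has variance s₁₂² + s₀² − 2·rho·s₁₂·s₀, where s₀ and s₁₂ are the baseline and week-12 SDs. The adjusted residual variance is s₁₂²(1 − rho²). The ratio of the two SDs is multiplied by 1.233/1.212 = 1.017 for the extra covariates.

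| week-12 SD | rho | SD of change | adjusted SD | width ratio |
|---|---|---|---|---|
| 1.25 | 0.5 | 1.087 | 1.083 | 1.01 (no gain) |
| 1.25 | 0.3 | 1.242 | 1.192 | 0.98 |
| 0.72 | 0.5 | 0.722 | 0.625 | 0.88 |
| 0.72 | 0.3 | 0.854 | 0.688 | 0.82 (18% narrower) |

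Simulation of the allocation agrees with all four rows.

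**3. Household pairs.** With k pairs among 44 subjects the variance rises by the factor 1 + ICC × 2k/44. At ICC 0.5 this is 1.023 (k = 1), 1.045 (2), 1.091 (4) and 1.227 (10). Simulated type I error of the week-12 t-test over ICC 0.1-0.5:

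| pairs | rho 0 | rho 0.3 | rho 0.5 |
|---|---|---|---|
| 2 | 5.2-5.7% | 4.4-4.9% | 3.2-3.5% |
| 4 | 5.1-6.0% | 4.5-5.1% | 3.6-4.1% |
| 10 (extreme) | 5.2-7.4% | 5.0-7.0% | 4.0-5.4% |

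With one pair (ICC 0.3 and 0.5) the range at rho 0 was 5.0-5.2%.

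**4. Covariates do not handle households.** The adjusted model without clustering gave 4.9-5.6% with one or two pairs, 5.2-6.0% with four and 5.4-7.8% with ten. It removes the conservatism that partly offsets the pairing, so the two changes belong together once there are about four pairs. Household-clustered CR2 standard errors gave 4.5-5.5%, and keeping one member per household gave 4.5-5.4%.

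**The case against.** The strongest reply is that a t-test after stratified randomisation is conventional and errs on the safe side when the strata are prognostic. Section 4.9 asks stratification for balance, and the design delivers it. That stands: with no pairs the t-test does not create false positives.

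A second reply is that Aim 1 is about reduction, so a change-score test may be meant and baseline is then already used. This stands in part. At a week-12 SD of 1.25 and rho 0.5 nothing would be gained. With equal SDs and rho 0.3-0.5 the change score still gives up 12-18% in interval width. Neither version uses the strata or the households.

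Three stronger readings are tempting, and the documents do not support them.
- *Adjustment would bring a much larger gain through a higher correlation.* With SDs of 0.72 and 1.25, rho 0.7 needs a slope of 0.7 × 1.25/0.72 = 1.21. Subjects would have to spread out from their baselines by more than one-for-one.
- *The t-test leaves the trial short of power.* At the planned 1.5 points and an SD of 1.25 (1.2 SD), 22 per arm give about 97% power.
- *The household rule inflates false positives.* Error near 7% needs 10 pairs, or 20 of the 44 completers, with ICC 0.5. Both members must separately meet the criteria in 4.1, and no pair count is given.

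**Conclusion.** The point holds in a modest form. The between-arm test in 4.7 ignores both allocation features in 4.3 and does not fix which quantity it tests. For the week-12 endpoint with no pairs, it is conservative (about 3-4.5% at rho 0.3-0.5), and adjustment narrows the interval by about 3-12%. Against a change score the gain runs from none to about 18%. Pairs act in the opposite direction, with at most about 6% type I error at four pairs.

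The sign and size of the net error therefore depend on the correlation, the SDs, the number of pairs and the ICC, and the documents state none of these. A reader might infer that the planned test is invalid or the trial at risk. The figures do not show that. This is a worthwhile but optional change, held with medium confidence.

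**What to change.** In 4.7, make the primary between-arm comparison a linear model for week-12 HgbA1c on arm, baseline HgbA1c (continuous) and the stratification factors. This also settles the choice between week-12 value and change. Fix it before unblinded data are seen.

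Record a household identifier for every subject, including the pilot-funded subjects in 4.7 ("of which 8 were eligible and 6 completed the entire study intervention"), and report the number of pairs per arm. If any pairs enrol, add a sensitivity analysis keeping one member per household. With about four or more pairs, use household-clustered standard errors with a small-sample correction instead (for example CR2 with Satterthwaite degrees of freedom). With no pairs, neither is needed.

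The cost is one data field and one model specification, with no extra subjects. If baseline proved not prognostic, the interval would be about 2% wider, or about 1 point of power. Clustering would widen the adjusted interval by a further 2-5% with four pairs.
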